## 10.5.7. Safety and Tolerability

Safety analyses will be descriptive in nature.

All reported adverse events will be coded to a standard set of terms using MedDRA coding dictionary (V19.1 or higher) treatment.

AEs and tolerability data will be presented descriptively by treatment and cohort. AEs will be tabulated by body system, preferred term, seriousness, severity and relation to study drug by cohort. Where applicable, changes in values over time (e.g., lab values, vital signs, electrocardiograms [ECGs]) will be presented, this will include clinical laboratory evaluations (including CBC, blood chemistry and urinalysis), coagulation (INR, PTT, PT), cytokines, vital signs, and ECGs. Shift tables of normal / abnormal versus baseline may be presented as well.

Draize scores will be presented in tabular format by visit, treatment, and cohort.

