- 5.4.2 This is a consecutive 4 cohort, dose escalation placebo-controlled clinical trial in overweight and obese subjects. All cohorts will be comprised of 6 active (RZL-012) and 2 placebo subjects.
- 5.4.3 Within each cohort, dosing of the first 3 subjects will progress consecutively from one individual to the other at 7-day intervals. For additional precaution, the first 3 subjects will be forced randomized into 2 active and 1 control. This study design will allow the physicians to monitor safety in a two subjects at each dose, nevertheless the blindness will remain intact. The remaining subjects in a cohort will be randomized to either active treatment or placebo in a ratio determined by the number of subjects targeted for each cohort. Dosing of the next subjects will be in couples and the last subjects will be in a triplet.

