  - 5.5.6 The planned sample size is 32 subjects (8 in each cohort). 6 subjects per dose group paradigm with the addition of a 2 subjects per control group for all doses. A maximum of 32 evaluable subjects will be included in the study (24 in the RZL-012 treatment arm and 8 in the placebo arm) and followed for as long as 3 months in the 2 lowest dose cohorts, and in the 2 highest dose cohorts for up to 5 months.
- 5.6 Statistical Analysis Software and Data Management
  - 5.6.1 Data manipulation, tabulation of descriptive statistics, calculation of inferential statistics, and graphical representations will be performed using SAS® version 9.3 or higher for Windows. If the use of other software is warranted, the final statistical methodology report will detail what software was used for what purposes.
  - 5.6.2 Data Management
  - 5.6.3 Data management for the study is performed by Spaulding Clinical.
  - 5.6.4 Medical Coding

- 5.6.5 Concomitant medications entered into the database are coded using the WHO (World Health Organization) Drug Public Website Dictionary named WHOCC-ATC/DDD index, which employs the Anatomical Therapeutic Chemical classification system.
- 5.6.6 Adverse events are coded using the most updated version of Medical Dictionary for Regulatory Activities (MedDRA) terminology.
- 5.6.7 Medical history events are coded using the most updated version of Medical Dictionary for Regulatory Activities (MedDRA) terminology
- 5.6.8 Handling of Missing data
- 5.6.9 No imputation of missing data will be performed
- 5.6.10 Protocol Violations and Deviations
- 5.6.11 Departures from the protocol should be avoided unless required for the safety of the subject. Protocol deviations and, if possible, the reason for occurrence will be documented by the study monitor and included in the final clinical study report.
- 5.6.12 The Investigator must report any protocol deviation to the Sponsor and, if required, to the IRB/IEC in accordance with local regulations, within reasonable time. All violations and deviations must be recorded in the study site's electronic system and signed by the Investigator (or designee).

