## 5.8 Statistical Analysis

- 5.8.1 General
- 5.8.2 All measured variables and derived parameters will be listed individually and, if appropriate, tabulated by descriptive statistics. For categorical variables summary tables will be provided giving sample size, absolute and relative frequency. For continuous variables summary tables will be provided giving sample size, arithmetic mean, standard deviation, standard error, coefficient of variation (CV%), median, minimum and maximum of variables, and 95% confidence intervals of means.
- 5.8.3 The data is analyzed using the SAS ® version 9.3 or higher (SAS Institute, Cary North Carolina). Analyses presented in the clinical report but not mentioned in the SAP are unplanned or ad-hoc analyses.
- 5.8.4 Statistical methods presented in the SAP may be slightly different from those that are presented in the protocol. Differences are clearly stated and the SAP supersedes the protocol only with regard to the way data will be handled and analysed.
- 5.8.5 Derived Data
- 5.8.6 Definition of baseline
- 5.8.7 Baseline is defined as the last non-missing value prior to the patient start of treatment (screening or baseline visit).
- 5.8.8 End of Study
- 5.8.9 The end-of-study visit is defined as Day 168.
- 5.8.10 Disposition of subjects (Table 14.1-1 14.1.2)
- 5.8.11 The number of subjects that are randomized into the study, the number of subjects in the Safety, efficacy analysis set, and PK populations, and the number of study completers will be presented.
- 5.8.12 The reasons for early termination/ withdrawal will be summarized.

- 5.8.13 Demographic and Baseline data (Tables 14.1-3-14.1-4)
- 5.8.14 Baseline and demographic data will be summarized in appropriate tables using the Safety population. The data includes demographic characteristics (age and gender) and medical history.
- 5.8.15 Efficacy Analysis
- 5.8.1 The primary endpoint for efficacy is a significant thermogenesis at the injected site compared with the contra-lateral, non-injected site.
- 5.8.2 The average temperature will be presented in a tabular form by visit, side (treated / not treated) and treatment received (RZL-012 / placebo) by cohort and overall. Difference between the sides (treated not treated) will be presented in a tabular form by visit treatment along with the change from baseline (net-delta) in these differences by cohort and overall.

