- 5.8.3 Kruskal-Wallis will be used to compare the net-delta between the study arms for the relevant cohorts and visits.
- 5.8.4 The number and percent of subjects with a thermogenic effect, defined as a net-delta ≥ 1, will be presented by cohort and visit for the subjects in the active arm. The duration of the thermogenic effect after the Day 28 visit, for subjects in the active arm with thermogenic effect at the Day 28 visit will be presented.
- 5.8.5 Subcutaneous Fat Mass (SFM) ratio (treated sites / control sites) averaged over the MRI slices will be presented in tabular form by visit, treatment and cohort. The change from baseline in this ratio (in % from the ratio at baseline) will be presented in the same manner, and compared between the treatment arms with Kruskal-Wallis test.
- 5.8.6 Changes from baseline in fasting blood glucose, lipid profile, anthropometric changes, inflammatory markers and cytokines will be presented by visit, treatment, and cohort.
- 5.8.7 Histology results will be presented in tabular form by treatment for relevant subjects.
- 5.8.8 Safety analysis
- 5.8.9 Safety data will be summarized for the Safety population.
- 5.8.10 Adverse events will be coded according to coding dictionaries (the most updated version of MedDRA) and presented in tables by System Organ Class (SOC) and Preferred Term (PT) and by treatment group.

- 5.8.11 The incidence of AEs, as well as the intensity and relationship to study drug will be summarized by treatment group.
- 5.8.12 The incidence of all adverse events will be presented by treatment overall and by cohort along with two sided 95% exact binomial Confidence Interval (CI).
- 5.8.13 The incidence of intolerable side effects will be presented by treatment overall and by cohort along with two sided 95% exact binomial Confidence Interval (CI).
- 5.8.14 Concomitant medication verbatim terms (as recorded on the CRFs) will be coded to Anatomical Therapeutic Chemical (ATC) Level 2 and 4 using the World Health Organization (WHO) dictionary.
- 5.8.15 Interim Analysis
- 5.8.16 An interim analysis is planned at the end of each cohort for evaluation of efficacy. For this purpose, a data lock (except for externally collected data such as PK) will be implemented after each cohort is completed. Upon lack of trends in efficacy due to effect size, the Sponsor will consider study termination

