14.2.2 PK Assessments

Table 14.2.2-1: Summary Statistics of RZL-012 Concentrations (ng/mL) by Treatment and time (hours)

Table 14.2.2-2: Summary of RZL-012 PK Parameters by Treatment

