14.3 Safety Data

14.3.1 Adverse Events

Table 14.3.1-1: Frequency of Any Adverse Events

Table 14.3.1-2: Frequency of any intolerable side effects

Table 14.3.1-3: Summary of Adverse Events by SOC and PT by treatment

Table 14.3.1-4: Summary of Adverse Events by SOC, PT, severity, and by treatment

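### The SAP breaks adverse events down by term, intensity and relatedness by treatment group only, where protocol 10.5.7 asks for cohort, so the planned summaries do not show which events rise with dose

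*SAP*

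**What the plan says.** Numbering restarts within SAP section 5.8, so several item numbers occur twice. Items 5.8.10 to 5.8.13 below are those under Safety analysis, and 5.8.3 and 5.8.4 are those under General.

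- **SAP 5.8.10 and 5.8.11.** Coded adverse events are "presented in tables by System Organ Class (SOC) and Preferred Term (PT) and by treatment group". Intensity and relationship to study drug are also split by treatment group. Neither item names cohort or dose.
- **SAP Appendix I, 14.3.1.** The SOC/PT shell (14.3.1-3) is by treatment, and so is the next: "Table 14.3.1-4: Summary of Adverse Events by SOC, PT, severity, and by treatment". No shell title covers seriousness or relatedness.
- **SAP 5.8.12 and 5.8.13.** The incidence of any adverse event and of intolerable side effects is given by treatment, overall and for each cohort, with exact binomial 95% intervals.
- **Protocol 10.5.7.** "AEs will be tabulated by body system, preferred term, seriousness, severity and relation to study drug by cohort". The synopsis says the same under Statistical Methods.
- **Protocol synopsis, Safety Analysis.** Safety data are to be summarised by treatment and cohort, but a later sentence tabulates adverse events over all subjects together and by treatment, without cohort.
- **SAP 5.8.4.** On departures from the protocol: "Differences are clearly stated and the SAP supersedes the protocol only with regard to the way data will be handled and analysed".

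**The concern.** This is a dose-escalation trial. Protocol 10.1 gives its purpose as finding the tolerated dose with the largest thermogenic effect, and the synopsis dose table runs from 40 to 180 mg. A reader of the report will want to know whether particular events become more frequent or more severe as the dose rises. Protocol 1.2.4 gives a concrete example: one phase 0 subject had a severe ALT and moderate AST elevation, and the sponsor undertook to watch liver function closely in the next trial.

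A programmer who follows 5.8.10 and 5.8.11 literally would produce two columns, 24 RZL-012 subjects and 8 placebo subjects. The by-cohort table of any adverse event does not replace the missing breakdown. Protocol 7.2 expects local reactions, so most subjects at every dose could have some event, and that table might then separate the doses poorly. By-cohort term tables produced later would count as unplanned under SAP 5.8.3, because the SAP does not mention them.

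**Working it through.** **1. What treatment group means.** The SAP does not define it. Three things point to the two arms:
- The efficacy item on average temperature glosses treatment received as RZL-012 or placebo, and names cohort separately.
- The efficacy items on the fat-mass ratio and on laboratory and anthropometric changes list treatment and cohort as separate factors.
- 5.8.12 and 5.8.13, directly after the items at issue, add cohort explicitly.

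Table titles alone settle nothing. Tables 14.3.1-1 and 14.3.1-2 also omit cohort, although the text requires it for them. The finding rests on the text of 5.8.10 and 5.8.11.

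**2. The plan's own numbers.** SAP 5.4.2: "This is a consecutive 4 cohort, dose escalation placebo-controlled clinical trial in overweight and obese subjects", and "All cohorts will be comprised of 6 active (RZL-012) and 2 placebo subjects". So 4 × 6 = 24, 4 × 2 = 8 and 24 + 8 = 32. This reproduces SAP 5.5.6 ("24 in the RZL-012 treatment arm and 8 in the placebo arm").

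**3. Ceiling on the dilution.** If x subjects have an event and all are in one cohort, the cohort rate is x/6 and the pooled rate x/24. The ratio is (x/6)/(x/24) = 24/6 = 4 for any x above 0. If escalation stops after k cohorts, the ceiling is 6k/6 = k.

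**4. Illustrative counts (assumed; the documents give none).** Exact 95% intervals are Clopper-Pearson: the lower limit is the 0.025 quantile of Beta(x, n−x+1), the upper the 0.975 quantile of Beta(x+1, n−x).

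| Event confined to one cohort | By cohort, n = 6 | Pooled, n = 24 |
|---|---|---|
| 1 subject | 16.7% (0.4-64.1) | 4.2% (0.1-21.1) |
| 3 subjects | 50.0% (11.8-88.2) | 12.5% (2.7-32.4) |
| 4 subjects | 66.7% (22.3-95.7) | 16.7% (4.7-37.4) |
| 6 subjects | 100% (54.1-100) | 25.0% (9.8-46.7) |

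In the 4-subject row, the other three cohorts together show 0/18 (0-18.5%).

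| Counts in cohorts 1, 2, 3, 4 | Top-dose rate | Pooled rate | Ratio |
|---|---|---|---|
| 0, 0, 2, 4 | 4/6 = 66.7% | 6/24 = 25.0% | 2.67 |
| 0, 1, 2, 4 | 4/6 = 66.7% | 7/24 = 29.2% | 2.29 |
| 0, 1, 2, 3 | 3/6 = 50.0% | 6/24 = 25.0% | 2.0 |
| 2, 2, 2, 2 | 2/6 = 33.3% | 8/24 = 33.3% | 1.0 |

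**5. PK, set side by side.** The shells are by treatment ("Table 14.2.2-2: Summary of RZL-012 PK Parameters by Treatment"), with no statement whether that means dose. On sampling in cohort 4, the protocol synopsis (Baseline visit) and 6.1.15 include all cohorts. Protocol Appendix I footnote f says all cohorts and then excludes the fourth. SAP footnote f limits sampling to cohorts 1 to 3.

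**The case against.** The strongest reply is that little is lost. The primary safety endpoint is the incidence of intolerable side effects and of all adverse events, and 5.8.12 and 5.8.13 keep both by cohort. Listing 16.2.7-1 gives individual events for at most 24 active subjects. Escalation rests on DSMB review of each cohort's safety data, not on end-of-study tables. The synopsis sentence without cohort matches the SAP, so the protocol is not of one voice. All of this stands and limits the consequence. It does not remove the gap, because a listing is not a planned summary and the detailed protocol section is explicit about cohort.

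Stronger readings a reader might infer, which the documents do not support:

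- *The primary safety endpoint is diluted.* It is not, for the reason just given.
- *Pooling makes a real signal indistinguishable from placebo.* Overlap of intervals does not show this: 4/24 (4.7-37%) overlaps placebo 0/8 (0-37%), but so does the unpooled 4/6 (22-96%).
- *The PK tables average over doses.* For drug concentrations, by treatment may well mean dose, since placebo subjects receive no RZL-012. Any figure for the resulting spread also depends on cohort 4. With six subjects per dose and strict proportionality, four cohorts give a mean dose of 105 mg and a CV of 50%. Cohorts 1 to 3 give a mean of 80 mg, SD √(6 × (40² + 0² + 40²)/17) = 33.6 and CV 42%.
- *The SAP loosened the PK analysis set.* SAP 5.7.5 repeats protocol 10.4.3.
- *The SAP certainly contradicts its source protocol.* The SAP cites protocol V1.4 of 4 March 2018. The available protocol is numbered 001.2 with pages dated 26 May 2017, so this cannot be confirmed.

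**Conclusion.** The point holds for the SOC/PT, intensity and relatedness summaries. Read on the SAP's own usage, they pool four dose levels, against protocol 10.5.7, without the statement of difference that 5.8.4 promises. Seriousness, which 10.5.7 also wants by cohort, is missing from 5.8.10, 5.8.11 and the shell titles. The understatement of a top-dose rate is at most four-fold, for an event confined to one of four filled cohorts. It is 2.0- to 2.67-fold for the assumed graded patterns and nil for a flat one.

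The conclusion assumes that treatment group means arm and that V1.4 kept the wording of 10.5.7. It covers planned summaries only: individual data remain available, and any-AE and intolerable-side-effect incidence remain by cohort. For PK, the documents support a request for clarification and no more.

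**What to change.** - In SAP 5.8.10 and 5.8.11 and Tables 14.3.1-3 and 14.3.1-4, tabulate by cohort (dose), with columns for pooled placebo, cohorts 1 to 4 and all RZL-012. Give seriousness and relatedness in the same layout, each with a shell.
- If two pooled columns are intended, say so as a departure from protocol 10.5.7 under 5.8.4 and give the reason.
- Check the wording against protocol V1.4, and bring the synopsis sentence that omits cohort into line with 10.5.7.
- State that by treatment in Tables 14.2.2-1 and 14.2.2-2 means dose cohort among RZL-012 recipients, and reconcile the passages on PK sampling in cohort 4.

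The cost is SAP wording, table shells and some programming. It needs no new data and no further subjects. SAP 5.1.2 has the plan finalised before hard lock, so the change belongs before that point.

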# 6. RELATED DOCUMENTS (OPTIONAL)

- 6.1 Study Protocol: RZL-012-P2aUS-001.4\_track changes 04 Mrch 2018
- 6.2 Randomization plan: RZL-012-P2aUS random plan final version 1.0 01-08-2017.pdf

## 7. RELATED FORMS (OPTIONAL)

Not Applicable

Medi Stat Statistics in Medicine	DOCUMENT NUMBER: 050-BST-PLN-001	PAGE: 28 of 31
TITLE: Statistical Analysis Plan		EFFECTIVE DATE: 14/Nov/2018 REVISION NUMBER: 2.0

#### 8. REFERENCES

Not Applicable

## 9. APPENDICES (OPTIONAL)

9.1 APPENDIX I: TABLE SHELLS

14.1 Demographic Data

Table 14.1-1: Disposition of Subjects

Table 14.1-2: Analysis populations

Table 14.1-3: Demographic Data

Table 14.1-4: Medical History

14.2 Efficacy Assessment

14.2.1 Primary Safety Endpoint

Table 14.2.1-1: Summary of Thermal Imaging per visit

Table 14.2.1-2: Summary of Thermal Imaging Changes per visit

P-value for difference between groups

Table 14.2.1-3: Frequency of Thermogenic Effect

Table 14.2.1-4: Duration of Thermogenic Effect

Table 14.2.1-5: Summary of MRI Results

14.2.2 PK Assessments

Table 14.2.2-1: Summary Statistics of RZL-012 Concentrations (ng/mL) by Treatment and time (hours)

Table 14.2.2-2: Summary of RZL-012 PK Parameters by Treatment

14.3 Safety Data

14.3.1 Adverse Events

Table 14.3.1-1: Frequency of Any Adverse Events

Table 14.3.1-2: Frequency of any intolerable side effects

Table 14.3.1-3: Summary of Adverse Events by SOC and PT by treatment

Table 14.3.1-4: Summary of Adverse Events by SOC, PT, severity, and by treatment

14.3.2 Other safety Assessments

Medi Stat Statistics in Medicine	DOCUMENT NUMBER: 050-BST-PLN-001	PAGE: 29 of 31
TITLE: Statistical Analysis Plan		EFFECTIVE DATE: 14/Nov/2018 REVISION NUMBER: 2.0

Table 14.3.2-1: Summary of Vital signs

Table 14.3.2-2: Changes from baseline - Vital signs

Table 14.3.2-3: Summary of Chemistry

Table 14.3.2-4: Changes from baseline – Chemistry

Table 14.3.2-5: Summary of Hematology

Table 14.3.2-6: Changes from baseline – Hematology

Table 14.3.2-7: Summary of Coagulation

Table 14.3.2-8: Changes from baseline – Coagulation

Table 14.3.2-9: Summary of Glucose

Table 14.3.2-10: Changes from baseline - Glucose

Table 14.3.2-11: Summary of Lipids

Table 14.3.2-12: Changes from baseline - Lipids

Table 14.3.2-13: Summary of Plasma

Table 14.3.2-14: Changes from baseline - Plasma

Table 14.3.2-15: Summary of Serum

Table 14.3.2-16: Changes from baseline – Serum

Table 14.3.2-17: Summary of Urinalysis

Table 14.3.2-18: Changes from baseline - Urinalysis

Table 14.3.2-19: Summary of Urinalysis - Categorical results

Table 14.3.2-20: Summary of Serology at Screening

Table 14.3.2-21: Summary of Drug Screening

Table 14.3.2-22: Summary of ECG Results

Table 14.3.2-23: Changes from baseline - Urinalysis

Table 14.3.2-24: Summary of Draize Score

Table 14.3.2-25: Summary of Physical Examination

Table 14.3.2-26: Any concomitant medications

Medi Stat Statistics in Medicine	DOCUMENT NUMBER: 050-BST-PLN-001	PAGE: 30 of 31
TITLE: Statistical Analysis Plan		EFFECTIVE DATE: 14/Nov/2018 REVISION NUMBER: 2.0

9.2 APPENDIX II: LISTINGS SHELLS

16.2.1 Subject Disposition

Listing 16.2.1-1: Subject Disposition

Listing 16.2.1-2: Visit dates per subject

16.2.2 Protocol Deviations

Listing 16.2.2-1: Inclusion/Exclusion Criteria

16.2.3 Subjects Excluded from the Efficacy Analysis

Listing 16.2.3-1: Subjects Excluded from the Efficacy and PK Analysis

16.2.4 Demographic Data and Baseline Assessments

Listing 16.2.4-1: Demographic Data

Listing 16.2.4-2: Medical History

16.2.5 Compliance/Exposure/Drug Concentration Data

Listing 16.2.5-1: Index Procedure

16.2.6 Individual Efficacy/PK/PD Response Data

Listing 16.2.6-1: PK Collection

Listing 16.2.6-2: Thermogenesis results

Listing 16.2.6-2: RZL-012 Concentration (ng/mL) by Subject, Treatment and Time

Listing 16.2.6-3: RZL-012 PK Parameters by subject and Treatment

Listing 16.2.6-5: MRI results

16.2.7 Adverse Events

Listing 16.2.7-1: Adverse Events

16.2.8 Laboratory and other safety parameters

Listing 16.2.8-1: Chemistry

Listing 16.2.8-2: Hematology

Listing 16.2.8-3: Coagulation

Listing 16.2.8-4: Urinalysis

Listing 16.2.8-5: CK, Total+Isoenzymes, and Serum

Listing 16.2.8-6: Plasma

Listing 16.2.8-7: Glucose

Listing 16.2.8-8: Lipids

Medi Stat Statistics in Medicine	DOCUMENT NUMBER: 050-BST-PLN-001	PAGE: 31 of 31
TITLE: Statistical Analysis Plan		EFFECTIVE DATE: 14/Nov/2018 REVISION NUMBER: 2.0

Listing 16.2.8-9: Drugs of Abuse

Listing 16.2.8-10: Serology

Listing 16.2.8-11: Vital Signs

Listing 16.2.8-12: ECG Findings

Listing 16.2.8-13: ECG Quantitative Results

Listing 16.2.8-14: Abnormal Physical Examination

Listing 16.2.8-15: Draize Assessment

Listing 16.2.8-16: Concomitant Medications
